13.5.3 Dose Escalation Rules

Dose escalation begins with enrollment of patients on the 0.003 mg/kg dose. The queue refers to the number of patients that have been allocated to doses, but have not yet completed the observation period. For safety purposes we want to keep the queue size moderate to prevent large numbers of patients being enrolled at any one time. Until 4 patients have complete DLT information the queue maximum is 2. After 4 patients have complete DLT information, the queue increases to 3. Patients cannot be enrolled for dose escalation if the queue maximum has been reached.

13.5.3.1 Starting Dose and Entry into the Study

Dose escalation begins with enrollment of patients on the 0.003 mg/kg dose (dose escalation will be conducted according to a CRM, as described in [Appendix 13.5](#)).

The queue refers to the number of patients that have been allocated to doses, but have not yet completed the observation period. For safety purposes we want to keep the queue size moderate to prevent large numbers of patients being enrolled at any one time. Until 4 patients have complete DLT information the queue maximum is 2. After 4 patients have complete DLT information the queue increases to 3. Patients cannot be enrolled for dose escalation if the queue maximum has been reached.

13.5.3.2 Assignment of Dose Level

The dose-toxicity model will be used to assign patients to doses. However, assignment of dose level is also governed by rules that govern the speed of dose escalation and rules that determine if untried dose levels may be skipped.

There must be complete DLT information through the first cycle (3 weeks) on at least 2 patients in order to escalate. When the dose is escalated, the dose level may increase by 100% as long as no toxicity events are observed. Once a non-DLT toxicity is observed, the dose may only be increased by 67%; and once a DLT is observed, the dose may only increase by 50%. In addition, the dose may never increase by more than 100% or by more than an absolute value of 1) 0.02 mg/kg at dose levels below 0.10 or 2) 0.10 mg/kg for dose levels between 0.10 and 0.30.

The increase in dose level is always constrained by the dose-toxicity model. The dose may never escalate to a dose that is considered unsafe.

13.5.4 Interim Monitoring

The trial is continuously monitored for safety and for success in identifying the MTD. If dose escalation is not stopped for either safety or success in identifying the MTD it will continue to enroll to the maximum sample size.

13.5.4.1 Safety Monitoring

The lowest dose (0.003 mg/kg) will be considered unsafe if it has a probability $< 25\%$ of a DLT rate $< 30\%$. The trial will stop, and no MTD found, if the lowest dose is considered unsafe (hence all doses are considered unsafe).

13.5.4.2 Success in Identifying the MTD

Dose escalation may be stopped early when sufficient information around the MTD has been obtained. We characterize this by having a sufficient number of patients at and around the MTD. We require at least 3 patients with complete information at the MTD and at least 6 patients with complete information within a certain interval around the MTD. If the MTD is 0.010 mg/kg or lower, we require 6 patients at the MTD. If the MTD is 0.011 mg/kg or greater, we require a total of 6 patients between the MTD and the dose level below.

[figure not shown]
13.5.5 Operating Characteristics

To evaluate how the dose escalation design performs, we simulated the study considering different dose-toxicity scenarios. We show operating characteristics of the trial based on 1,000 simulations per scenario. For each scenario we plot the mean sample size and cumulative probability of MTD across the 33 dose levels including all dose levels from:

- 0.003 to 0.02 mg/kg in increments of 0.001
- 0.02 to 0.05 mg/kg in increments of 0.005
- 0.05 to 0.10 mg/kg in increments of 0.01
- 0.10 to 0.30 mg/kg in increments of 0.05

[figure not shown]
The true DLT scenario is shown for reference along with a line indicating a 30% DLT rate. We further summarize the performance of the dose escalation design by showing the mean sample size and the 10%, 20%, 50%, 80%, and 90% quantiles of the cumulative MTD curve.

13.5.5.1 All Doses Safe

[figure not shown]
| Quantile of Cumulative MTD Selection | | | | | | |
|--------------------------------------|--------|------|------|------|------|------|
| True MTD | Mean N | 10% | 20% | 50% | 80% | 90% |
| 0.3 | 38 | 0.25 | 0.30 | 0.30 | 0.30 | 0.30 |

13.5.5.2 MTD is the Highest Dose (0.30 mg/kg)

[figure not shown]
| Quantile of Cumulative MTD Selection | | | | | | |
|--------------------------------------|--------|------|------|------|------|------|
| True MTD | Mean N | 10% | 20% | 50% | 80% | 90% |
| 0.30 | 38.3 | 0.10 | 0.15 | 0.20 | 0.30 | 0.30 |

13.5.5.3 MTD is a Middle Dose (0.15 mg/kg)

[figure not shown]
| True MTD | Mean N | Quantile of Cumulative MTD Selection | | | | |
|----------|--------|--------------------------------------|------|------|------|------|
| | | 10% | 20% | 50% | 80% | 90% |
| 0.15 | 35.6 | 0.10 | 0.10 | 0.15 | 0.15 | 0.20 |

13.5.5.4 MTD is a Middle Dose (0.10 mg/kg)

[figure not shown]
| Quantile of Cumulative MTD Selection | | | | | | |
|--------------------------------------|--------|------|------|------|------|------|
| True MTD | Mean N | 10% | 20% | 50% | 80% | 90% |
| 0.1 | 34.9 | 0.07 | 0.09 | 0.10 | 0.10 | 0.15 |

13.5.5.5 MTD is a Low Dose (0.05 mg/kg)

| Quantile of Cumulative MTD Selection | | | | | | |
|--------------------------------------|--------|------|------|------|------|------|
| True MTD | Mean N | 10% | 20% | 50% | 80% | 90% |
| 0.05 | 34.2 | 0.04 | 0.05 | 0.06 | 0.07 | 0.08 |

[figure not shown]
13.5.5.6 MTD is a Low Dose (0.02 mg/kg)

| True MTD | Mean N | Quantile of Cumulative MTD Selection | | | | |
|----------|--------|--------------------------------------|-------|-------|-------|------|
| | | 10% | 20% | 50% | 80% | 90% |
| 0.02 | 32.6 | 0.013 | 0.018 | 0.020 | 0.025 | 0.03 |

13.5.5.7 No Doses Safe

In this scenario, there is a 61% probability of stopping early for safety. The lowest dose is selected as the MTD with 37% probability.

13.6 Appendix: Clinical Case Definitions: Level 1 of Diagnostic Certainty for Guillain-Barré Syndrome

- Bilateral AND flaccid weakness of the limbs^{1,2,3}
AND
- Decreased or absent deep tendon reflexes in weak limbs⁴
AND
- Monophasic illness pattern⁵ AND interval between onset and nadir of weakness between 12 h and 28 days AND subsequent clinical plateau⁶
AND
- Electrophysiologic findings consistent with GBS⁷
AND
- Cytoalbuminologic dissociation (i.e., elevation of CSF protein level above laboratory normal value AND CSF total white cell count <50 cells/ μ L)⁸
AND
- Absence of an identified alternative diagnosis for weakness⁹.

Reference: Sejvar 2011¹³

¹ Weakness is usually, but not always, symmetric in nature, and usually has a pattern of progression from legs to arms (ascending). However, other patterns of progression may occur (e.g., beginning in the arms). The degree of weakness can range from mild to moderate to severe, i.e., complete paralysis.

² Respiratory or cranial nerve-innervated muscles may also be involved.

³ It is important that strength be assessed in a manner that takes into account subject age, sex, and level of functioning.

⁴ Decreased or absent tendon reflexes may also be seen in limbs without weakness. However, to meet case definition criteria, decreased or absent tendon reflexes must be observed in weak limbs.

⁵ Fluctuations in level of weakness, before reaching nadir, or during the plateau or improvement phases, occur in some cases, usually associated with the use of disease-modifying therapies. Such fluctuations usually occur within the first 9 weeks after onset and are followed by eventual improvement.

⁶ The eventual outcome is either stabilization at nadir OR subsequent improvement OR death.

⁷ Electrophysiologic patterns consistent with polyneuropathy of the types described for GBS. Electrophysiologic studies performed sooner than 7 days after weakness onset may be normal and should thus be repeated at a later time if possible, and “normal” studies may occur in otherwise typical cases of GBS. However, cases with persistently “normal” studies will not meet Level 1 criteria.

⁸ CSF (cerebrospinal fluid) protein concentrations should be elevated above what is considered normal reference values for the testing laboratory. CSF may be “normal” in otherwise typical cases of GBS; this is particularly true within the first week of illness. However, cases with persistently “normal” CSF, or CSF with ≥ 50 WBC, will not meet Level 1 criteria.

⁹ If an alternative diagnosis explaining flaccid weakness/paralysis is present a diagnosis of Guillain-Barré syndrome is excluded. However, in many, if not most cases, a comprehensive documentation of testing for various other etiologies will either be incomplete or unavailable. These case definitions are provided to give guidance in the absence of detailed information on investigations for alternative etiologies of flaccid paralysis.

13.7 Appendix: Guillain–Barré Syndrome Disability Scale

| Score | Description |
|-------|--|
| 0 | Healthy |
| 1 | Minor symptoms or signs of neuropathy but capable of manual work/capable of running |
| 2 | Able to walk without support of a stick (5m across an open space) but incapable of manual work/running |
| 3 | Able to walk with a stick, appliance, or support (5m across an open space) |
| 4 | Confined to bed or chair bound |
| 5 | Requiring assisted ventilation (for any part of the day or night) |
| 6 | Death |

Reference: Sejvar 2011¹³

## 1 Introduction

This statistical analysis plan (SAP) describes the statistical methods to be used during the reporting and analyses of data collected under ADC Therapeutics Protocol ADCT-301-001.

This SAP should be read in conjunction with the study protocol and case report form (CRF). This version of the plan has been developed using the protocol Amendment 9 dated 04 January 2019 and CRF version PROD 10.0 dated 29 March 2018.

[figure not shown]
## 2 Study Objectives

### 2.1 Primary Objectives

- Evaluate the safety and tolerability and determine the maximum tolerated dose (MTD) of ADCT-301 in subjects with relapsed/refractory lymphoma (Part 1).
- Determine the recommended dose of ADCT-301 for Part 2 (expansion).
- Evaluate the safety and tolerability of ADCT-301 in Part 2 at the dose level recommended in Part 1.

### 2.2 Secondary Objectives

- Evaluate the activity of ADCT-301 measured by overall response rate (ORR), duration of response (DOR), progression-free survival (PFS), and overall survival (OS).
- Characterize the pharmacokinetic (PK) profile of HuMax-TAC (total antibody; drug-to-antibody ratio [DAR]  $\geq 0$ ), pyrrolobenzodiazepine (PBD)-conjugated HuMax-TAC (DAR  $\geq 1$ ), and free warhead SG3199.
- Evaluate anti-drug antibodies (ADAs) in blood before, during, and after treatment with ADCT-301.

### **3 Study Design**

This is a Phase 1, first in human (FIH), open-label, dose-escalation (Part 1) and expansion (Part 2) study of ADCT-301 in patients with relapsed and refractory lymphoma. The study will evaluate the safety and tolerability of ADCT-301 as monotherapy, as well as the preliminary activity, PK, PD, and formation of ADAs of ADCT-301 in patients. The patient population includes those with relapsed or refractory histologically confirmed non-Hodgkin lymphoma (NHL; including Stage  $\geq$ Ib cutaneous T-cell lymphoma [CTCL]) or Hodgkin lymphoma (HL).

In Part 1, patients will receive ADCT-301 administered as a 2-hour intravenous infusion on Day 1 of each 3-week cycle. The initial dose level for Part 1 will be 3  $\mu$ g/kg. The highest possible dose will be 300  $\mu$ g/kg. The MTD will be the highest safe dose that has at least a 60% probability that the dose-limiting toxicity (DLT) rate is less than 30%.

Dose escalation will be conducted according to a continual reassessment method (CRM). Dose levels from 3 to 300  $\mu$ g/kg are possible, but the final dose level and number of doses will be dependent on the emergent toxicity profile and will be decided by a Dose Escalation Steering Committee (DESC). PK and PD evaluations may also inform decision making. See separate DESC Plan document.

The DLT period for dose escalation is changed from 2 cycles to 1 cycle in protocol amendment 4. However, the adaptive dose-escalation algorithm will incorporate cumulative DLTs occurring through Cycle 3. No intra-patient dose escalation will be allowed during the study. However, once the recommended Part 2 dose is determined, patients receiving lower dose levels of ADCT-301 may be offered continued treatment at the recommended dose.

During Part 1, the DESC may expand enrollment at doses below the current dose level being evaluated as part of the dose escalation process. Additional patients may only be added at a lower dose level provided there is at least 1 patient with documented stable disease. Not more than 10 patients in total can be treated at any dose level unless at least 3 of the 10 patients have documented partial response or better using the 2014 Lugano Classification criteria or other appropriate measures of response.

In Part 2 (expansion), patients will be assigned to receive the recommended dose(s) of ADCT-301, as determined by the DESC during Part 1 of the study. The patient population (e.g., disease subtypes) to be enrolled in Part 2 (expansion) may be refined based on results and observations from Part 1. Different recommended dose(s) for expansion may be defined and carried forward into part 2 for different lymphoma subtypes.

#### **3.1 Sample Size Consideration**

This is a Phase 1 study with a maximum total sample size of 140 patients. Part 1 will enroll approximately 80 patients and Part 2 will enroll approximately 60 patients.

#### **3.2 Randomization**

This study is not randomized.

### **3.3 Modifications to the statistical section of the protocol**

The efficacy analysis set was defined in the protocol as all patients with valid baseline data who receive at least 2 doses of study drug or who have documented progression of disease at any time after the first dose of study drug. The efficacy analysis set is updated in the SAP to include all patients who have received at least one dose of ADCT-301 with a valid baseline and at least one valid post-baseline disease assessment or patients who have documented progression of disease or death at any time after the first dose of study drug.

## 4 Statistical methods

All analyses use SAS® version 9.4 or higher. Summary tables will be organized by each dose level; if some dose levels have few patients, then dose levels could be combined into dose ranges. All available data will be used in the analyses, and important data will be included in data listings, sorted by dose level, patient, and by visit within patient. Missing data will not be imputed, except via censoring in survival analyses and as otherwise specified.

Unless otherwise noted, categorical data will be presented using counts and percentages, with the number of patients in the analysis set by treatment group as the denominator for percentages. Percentages will be rounded to one decimal place, except 100% will be displayed without any decimal places and percentages will not be displayed for zero counts. Continuous data, unless otherwise noted, will be summarized using the number of observations (n), mean, standard deviation (std), median, minimum, and maximum. Minima and maxima will be rounded to the precision of the original value, and means, medians, and 95% confidence intervals (CIs) if presented will be rounded to 1 decimal place greater than the precision of the original value. The std will be rounded to 2 decimal places greater than the precision of the original value, up to a maximum of 3 decimal places.

No hypothesis testing will be performed in this study.

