4.1.2 Dose Expansion (Part 2)

In Part 2 (expansion), patients will be assigned to receive the recommended dose(s) of ADCT-301, as determined by the DESC during Part 1 of the study.

The following dosing regimen(s) may be investigated based on safety and PK emerging information:

- 45 µg/kg every 3 weeks for 3 cycles followed by 30 µg/kg every 3 weeks for patients who have not progressed.
- 45 µg/kg every 3 weeks for 3 cycles followed by 20 µg/kg every 3 weeks for patients who have not progressed.
- 45 µg/kg every 3 weeks for 4 cycles followed by 30 µg/kg every 3 weeks for patients who have not progressed.
- 45 µg/kg every 3 weeks for 4 cycles followed by 20 µg/kg every 3 weeks for patients who have not progressed.

The patient population (e.g., disease subtypes) to be enrolled in Part 2 (expansion) may be refined based on results and observations from Part 1.

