8.6.2.2 Clinical Laboratory Results

Clinical hematology, biochemistry, and urinalysis data will be summarized at each scheduled assessment. Numeric hematology and biochemistry results will be summarized using change from baseline. All results will be summarized using shift from baseline. Shifts for clinical laboratory results that can be graded according to CTCAE Version 4.0 will be summarized by CTCAE grade. Shifts for other numeric laboratory results will be by high/normal/low flag. Shifts for all other laboratory results will be by normal/abnormal flag.

Summaries by visit will include data from scheduled assessments, and all data will be reported according to the nominal visit date for which it was recorded. Unscheduled data will be included in “worst case post baseline” summaries, which will capture a worst case across all scheduled and unscheduled visits after the first dose of study treatment. Further details will be provided in the SAP.

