### 4.1 Analysis Sets

#### 4.1.1 Safety Analysis Set

The safety analysis set consists of all patients who receive ADCT-301.

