### General common rules

All safety analyses will be performed on the safety analysis set, unless otherwise specified, using the following common rules:

- The baseline value is defined as the last non-missing value or measurement taken up to the first dose in the study.
- The analyses of the safety variables will be essentially descriptive and no systematic testing is planned.
- If relevant, selected safety analyses will be summarized by age, sex, racial subgroups, and any pertinent subgroups.
- The toxicity grade according to the Common Terminology Criteria for Adverse Events (CTCAE) version 4.0 will be taken into account in the summary. For patients with multiple occurrences of the same event, the maximum grade is used. If a patient has both missing and non-missing severity grades for treatment-emergent adverse events (TEAEs) within the same preferred term (PT), the patient will be counted under the non-missing severity grade.

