#### **4.8.3 Laboratory Data**

Laboratory data of hematology, biochemistry, coagulation, and urinalysis up to the end of study visit will be reported in SI units.

Descriptive statistics (mean, standard deviation, median, and range) will be calculated for the raw data and for their changes from baseline at each scheduled assessment for hematology, biochemistry, coagulation. All results will be summarized using shift from baseline. Shifts for clinical laboratory results that can be graded according to CTCAE version 4.0 will be summarized by CTCAE grade.

Summaries by visit will include data from scheduled assessments, and all data will be reported according to the nominal visit date for which it was recorded. Unscheduled data will be included in “worst case post-baseline” summaries, which will capture a worst case across all scheduled and unscheduled visits after the first dose of study treatment.

Summary analyses will include data up to the start of subsequent anticancer therapy/procedure.

All laboratory data, including urinalysis, will be listed. Pregnancy test results will not be listed, but will be included in datasets.

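### By default, any by-visit laboratory shift percentage would be divided by all treated patients, and so would understate the rate among patients still assessed at later cycles

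*SAP*

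**What the plan says.** SAP section 4 gives a general rule for categorical data. It opens "Unless otherwise noted, categorical data will be presented using counts and percentages", and the denominator is fixed "with the number of patients in the analysis set by treatment group as the denominator for percentages". The same section says "Missing data will not be imputed, except via censoring in survival analyses and as otherwise specified".

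SAP 4.8 (General common rules) adds "All safety analyses will be performed on the safety analysis set, unless otherwise specified", and SAP 4.1.1 reads "The safety analysis set consists of all patients who receive ADCT-301". That set does not shrink as patients stop treatment.

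For laboratory data, SAP 4.8.3 plans shifts from baseline for all results: "Shifts for clinical laboratory results that can be graded according to CTCAE version 4.0 will be summarized by CTCAE grade". It also describes summaries by visit built from scheduled assessments, and a separate worst-case post-baseline summary that includes unscheduled values. It names no denominator for any of these. Protocol 8.6.2.2 says "Clinical hematology, biochemistry, and urinalysis data will be summarized at each scheduled assessment".

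SAP 4.8.4 counts QTc categories at any time after baseline rather than by visit.

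**The concern.** Laboratory samples belong to treatment visits and the End of Treatment visit; the schedule in Protocol 13.1.1 has none in long-term follow-up. An abnormal value at, say, Cycle 5 can therefore be seen only in a patient still attending. If the count is divided by everyone ever treated at that dose level, a patient with no sample is in effect scored as having no abnormality.

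Safety and tolerability are primary objectives in both parts. A by-visit table built this way could make laboratory toxicity look milder at later cycles than it is among the patients still exposed. It could also distort comparison between dose levels if patients leave faster at some than at others. Renal and urine results matter here because Protocol section 2 lists nephrotoxicity among the nonclinical findings.

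**Working it through.** **Is a by-visit categorical table planned?** In SAP 4.8.3 the phrase about each scheduled assessment attaches to means, medians and ranges for hematology, biochemistry and coagulation. The sentences on shifts name no visit. Protocol 8.6.2.2 goes further, because it includes urinalysis among the data summarized at each assessment but limits change from baseline to numeric hematology and biochemistry. Urinalysis may be a dipstick (Protocol 7.3.4.3), and the SAP's by-visit descriptive statistics omit it. A per-assessment urinalysis summary is therefore most naturally a categorical shift. SAP 4.8.3 also keeps by-visit summaries apart from worst-case ones, so the second does not replace the first. By-visit shifts are the natural reading, but an inferred one.

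**Inputs.**
- Denominator N: all treated patients in the group (SAP 4, 4.8 and 4.1.1).
- Patients with no value: not imputed (SAP 4), so they add nothing to the numerator.
- Fraction assessed: falls over time, because treatment is open-ended (Protocol 4.1) and laboratory summaries stop at subsequent anticancer therapy (SAP 4.8.3).
- Retention per cycle q and rate among those assessed r: not in the documents. Assumed q = 0.95, 0.85 or 0.75 and constant r = 20%, with all patients assessed at Cycle 1.

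The plan states no figure on this point to reproduce.

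**Formula.** With n_c patients assessed at cycle c,

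displayed % = r × n_c / N = r × q^(c−1).

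At Cycle 4: 20% × 0.95³ = 17.1%; 20% × 0.85³ = 12.3%; 20% × 0.75³ = 8.4%.

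| Retention per cycle | Cycle 1 | Cycle 2 | Cycle 4 | Cycle 6 | Cycle 8 |
|---|---|---|---|---|---|
| 95% | 20.0 | 19.0 | 17.1 | 15.5 | 14.0 |
| 85% | 20.0 | 17.0 | 12.3 | 8.9 | 6.4 |
| 75% | 20.0 | 15.0 | 8.4 | 4.7 | 2.7 |

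The result does not depend on N. In whole patients: 2 of 10 at Cycle 1 is 20%. If 5 are assessed later and 1 has the shift, the table shows 1/10 = 10%, while the rate among those assessed is 1/5 = 20%.

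**Masking.** For the displayed figure to stay at 20%, the rate among those assessed must be 20% / q^(c−1). At Cycle 4 that is 23.3%, 32.6% or 47.4% for q = 0.95, 0.85 or 0.75. At 85% retention it is 62.4% by Cycle 8. A real rise of that size would look flat.

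**With the matching denominator.** Dividing by n_c returns r, here 20.0% at every cycle whatever the retention.

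**The case against.** The strongest reply has five parts.

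- **The rule is only a default.** This stands. A reader might infer that the SAP divides every percentage by the full set, but the rule yields wherever a section says otherwise. SAP 4.9.1, for example, restricts the SPD and mSWAT summaries to available data. That example also shows how an exception could have been written, and SAP 4.8.3 contains none.
- **By-visit shift tables are inferred.** This stands as a limit on certainty. If shifts were shown only as worst case, no by-cycle trend could arise.
- **The plan lets a reader see the effect.** This partly stands. Counts accompany percentages, continuous summaries give n, Protocol 8.6.4 tabulates patients dosed by cycle, and all laboratory data are listed. A careful reader could reconstruct the rate, but the printed percentage would still be diluted.
- **Little rests on these tables.** This stands and limits the importance. Clinically significant laboratory values are also recorded as adverse events (Protocol 7.3.4), where an all-treated denominator is suitable. Dose decisions rest on the continual reassessment method and the steering committee, and no hypothesis is tested.
- **Patients with a value are a selected group too.** This stands. Those removed for toxicity leave that denominator, and it becomes small. With 10 patients at a dose level and 75% retention, about 4 remain at Cycle 4 and about 1 at Cycle 8. This is a reason to show n; it does not justify counting unobserved patients as normal.

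**Conclusion.** The point holds in a limited form. Under the default rule, any by-visit laboratory shift percentage understates the rate among patients assessed by exactly the fraction not assessed. That follows from the rule itself and needs no assumption about rates. How much it understates cannot be computed from the documents; the 17.1%, 12.3% and 8.4% at Cycle 4 rest on assumed retention and an assumed constant 20%.

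Three stronger readings are not supported.

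- Displayed percentages need not fall with each cycle. They do so if the rate among those assessed is roughly constant, but a rising rate could offset or reverse the fall.
- QTc and worst-case tables have no by-cycle trend. They are affected only by patients with no evaluable value.
- A reader might expect attrition to mimic better tolerability after a Part 2 step-down such as "45 µg/kg every 3 weeks for 3 cycles followed by 30 µg/kg every 3 weeks for patients who have not progressed". Protocol 4.1.2 says only that these regimens may be investigated, and the SAP plans no comparison before and after a step-down.

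The impact is on descriptive safety tables only. The change is still worth making, because the stated rule gives a misleading figure and the correction is cheap.

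**What to change.** In SAP 4.8.3, say whether laboratory shifts are shown by visit, as worst case, or both. Then set the denominators:

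- **By-visit shifts:** patients with a baseline value and a value at that visit, with that n printed beside each percentage. Alternatively, keep the full set and add a row for missing values.
- **Worst-case shifts (4.8.3) and QTc categories (4.8.4):** patients with at least one post-baseline value, plus a baseline value where a shift or change is shown.

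The cost is a sentence or two in the SAP and a change to the table shells; no new data are needed. The drawback is that late-cycle percentages will rest on few patients, all still on treatment, so n must be visible and those figures read with care.
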